8.1 Study Visits

8.1.1 Screening

Screening, to verify inclusion and exclusion criteria, will include:

1. obtaining written informed consent from patient or legally authorised representative (Section 8.2.1.1)
2. Review of eligibility criteria
3. documentation of demographics and medical history (Section 8.2.1.2)
4. Complete physical examination (Section 8.2.2.1)
5. vital signs (Section 8.2.2.2)
6. ECOG performance status (Section 8.2.2.3)
7. 12-lead electrocardiogram (ECG; Section 8.2.2.4)
8. clinical chemistry, coagulation profile and haematology (Section 8.2.2.45)
9. CEA and CA 19-9 analysis, backup plasma sample (Section 8.2.3.2)
10. pregnancy test (serum or urine) for female patients of child-bearing potential (Section 8.2.1.3); patients with positive results will be discontinued from the study with no further study procedures performed
11. CT/MRI/PET scan of chest and abdomen with tumor measurement and evaluation by RECIST 1.1 criteria (Section 8.2.3.3)
12. documentation of prior and concomitant medications (Section 7.7)
13. Histological confirmation

Patients who meet the inclusion/exclusion criteria (Section 6) will be randomized to one of the following:

1. Treatment arm (Regorafenib + Durvalumab)
2. Control arm

8.1.2 Treatment Phase: Table 2 and 3.

Patients allocated to regorafenib + durvalumab arm will undergo visits every week for the first cycle, every 2 weeks for the second cycle, and monthly thereafter.

Patients allocated to the control group will undergo visits every 12 weeks.

If at any time a relapse is confirmed, the patient will discontinue treatment. Patients in the control arm will be offered to crossover to regorafenib plus durvalumab.

All visits have a window of ± 7 days.

- Patients allocated to Treatment arms will undergo the following procedures and assessments:

At each visit:

1. Limited physical examination
 2. vital signs
 3. ECOG performance status
 4. Weight
 5. Clinical chemistry and haematology (CBC + differential platelet count; creatinine; total bilirubin; AST; ALT; alkaline phosphatase; LDH; albumin; glucose; potassium; sodium; calcium)
 6. administration of therapy (regorafenib plus durvalumab at Day 1 of every cycle)
 7. documentation of AEs/SAEs
 8. documentation of concomitant medications and procedures (at Day 1 of every cycle)
 9. CEA and CA19-9 analysis and CT/MRI/PET scan as per baseline assessment: every 12 weeks. From day 1 (\pm 7 days).
- Patients allocated to no further treatment (Control Group) will undergo the following procedures and assessments:
at each visit (every 12 weeks.)
 1. physical examination
 2. vital signs
 3. ECOG performance status
 4. Weight
 5. pregnancy test (serum or urine) for female patients of child-bearing potential
 6. Clinical chemistry and haematology (CBC + differential platelet count; creatinine; total bilirubin; AST; ALT; alkaline phosphatase; LDH; albumin; glucose; potassium; sodium; calcium)
 7. documentation of AEs/SAEs
 8. documentation of concomitant medications and procedures
 9. CEA and CA 19-9 analysis
 10. CT/MRI/PET scan as per baseline assessment

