Tumor imaging/ response assessments ^c	X	X		X
Hematology ^d	X	X		X
Chemistry ^d	X	X		X
Biomarkers ^d	X	X		X
AEs assessments	X	X	X	X
Survival and anti-cancer therapy			X	X

Abbreviation: CBC: cell blood count; RBC: red blood cell; WBC: White blood cell; aPTT: activated partial thromboplastin time; PT: prothrombin time; INR: international normalized ratio; AST: Aspartate aminotransferase; ALT: alanine aminotransferase; LDH: Lactate dehydrogenase; β -hCG: beta-human chorionic gonadotropin; Na: sodium; K: potassium; Cl: chloride; Mg: magnesium; Ca: calcium; P: phosphate; CEA: Carcinoembryonic antigen; Ca 19-9: Carbohydrate antigen 19-9; ECOG PS: Eastern Cooperative Oncology Group Performance Status; ECG: electrocardiogram; AEs: adverse events

a) Vital signs and Physical examination

Patients will have a complete physical exam to include an examination of major body systems and an assessment for emergent toxicities or changes from prior visits. Limited physical examination should be performed symptom-directed.

Examinations will be conducted by a physician, trained physician's assistant, or nurse practitioner, as acceptable according to local regulation.

Vital signs include: blood pressure and heart rate, body temperature, respiratory rate.

b) Electrocardiogram (ECG)

Perform a 12-lead resting electrocardiogram (ECG) before the beginning of the treatment, at the end-of-treatment and if clinically indicated. Patients should be in a supine position for at least 10 min before recording. ECG tracings will be reviewed by a qualified physician for assessment of QT interval as well as signs of qualitative abnormalities, including evaluation of rhythm, ST segment morphology, T wave morphology, and presence/absence of U wave.

The original ECG tracing will be maintained in the source documentation of each patient.

c) Tumor imaging/ response assessments

Including computed tomography (CT) scan / magnetic resonance imaging (MRI) / PET scan. The same radiographic procedure should be used throughout the study for each patient.

Tumor assessment should be performed every 12 weeks \pm 1 week for the first year (relative to the date of randomization), every 16 \pm 1 week in the second year and then every 24 weeks \pm 1 week thereafter until RECIST 1.1-defined radiological PD or death (whichever comes first).

d) Local laboratory assessments will include the following:

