2.3 The different ways to reach the NED state

2.3.1 Surgery.

Based on current evidence[23], a number of concepts are widely accepted:

- a. the primary aim of treatment is achieving long term RFS following resectability;

- b. assessment of resectability should be performed with high quality cross-sectional imaging, staging the liver with magnetic resonance imaging and/or abdominal computed tomography (CT), depending on local expertise, staging extrahepatic disease with thoracic and pelvic CT, and in selected cases fluorodeoxyglucose positron emission tomography with ultrasound (preferably contrast-enhanced ultrasound) for intraoperative staging;
- c. optimal first-line chemotherapy –doublet or triplet chemotherapy regimens combined with targeted therapy– is advisable in potentially resectable patients;
- d. in this situation, at least four courses of first-line chemotherapy should be given, with assessment of tumor response every 2 months;
- e. response assessed by RECIST criteria [24] (conventional chemotherapy) or non-size-based morphological changes (antiangiogenic agents) is clearly correlated with outcomes; no imaging technique is currently able to diagnose accurately complete pathological response;
- f. duration of chemotherapy should be as short as possible and resection achieved as soon as technically possible in the absence of tumor progression;
- g. number of metastases or patient age should not be an absolute contraindication to surgery combined with chemotherapy;
- h. for synchronous metastases, it is not advisable to undertake major hepatic surgery during surgery for removal of the primary CRC; the reverse surgical approach (liver first) produces as good an outcome as the conventional approach in selected cases;
- i. for patients with resectable CRC liver metastases, perioperative chemotherapy may be associated with modest improved RFS;
- j. whether initially resectable or unresectable, cure is possible after complete resection of the metastases and MDT treatment is essential for improved clinical outcome and survival [23].

The surgical approach to limited liver metastases has produced a 40 and 20 % OS at 5 and 10 years and a DFS of 20 and 12% at the same long terms, respectively[6].

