8.1.4 Follow-up

During the early follow-up phase (Month 13-Month 24, Table 2 and 3) all patients will undergo the following visits every 3 months.

During the late follow-up phase (Month 25 to Month 60) all patients will undergo the following visits every 4-6 months.

1. Safety assessments
2. Physical examination
3. Vital signs
4. Eastern Cooperative Oncology Group [ECOG] performance status
5. CT/MRI/PET scan as per Investigator's choice
6. CEA and CA 19-9 analysis
7. Clinical chemistry and haematology (CBC + differential platelet count; creatinine; total bilirubin; AST; ALT; alkaline phosphatase; LDH; albumin; glucose; potassium; sodium; calcium; amylase; lipase)
8. Concomitant medications
9. For patients with documented relapse: visit (according to SoC) or telephone contact to document OS.

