8.2.3.3 Computed tomography and magnetic resonance imaging

CT/MRI/PET scans will be done to detect relapse, as specified by the objectives and endpoints of the study, and to confirm a diagnosis of relapse at any time during the study (Section 3.3.1).

While scans will be done as per SoC of the facility, minimal standards for CT/MRI/PET procedures will be provided. Data from CT/MRI/PET scans done at any times other than those specified for this study, i.e., done as part of SoC of the facility, will be collected for the eCRF.

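### The only scan field the protocol states is chest and abdomen, so pelvic imaging is not required at screening or in the treatment phase, although pelvic recurrence is a DFS event

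*Combined protocol and SAP*

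**What the plan says.** **Screening.** Section 8.1.1, item 11, asks for a "CT/MRI/PET scan of chest and abdomen with tumor measurement and evaluation by RECIST 1.1 criteria". No other trial procedure names a body region.

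**Treatment phase (8.1.2).** The experimental arm has "CEA and CA19-9 analysis and CT/MRI/PET scan as per baseline assessment: every 12 weeks". The control list has "CT/MRI/PET scan as per baseline assessment". Footnote c to the schedule tables adds that "The same radiographic procedure should be used throughout the study for each patient", without naming a region.

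**Later scans.** The end-of-treatment list (8.1.3) asks for tumour imaging and gives no region. From month 13 (8.1.4) the wording is "CT/MRI/PET scan as per Investigator's choice".

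**Standards.** Section 8.2.3.3 says: "While scans will be done as per SoC of the facility, minimal standards for CT/MRI/PET procedures will be provided". Those standards are not in the documents. The opening of section 8 treats any procedure not listed as the facility's own standard of care and outside the study, though the resulting CT and CEA data are to be recorded.

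**What the scans must support.** Eligibility (6.2) covers colorectal adenocarcinoma, with no exclusion of rectal primaries. Section 2.4 defines NED after surgery as removal of all visible lesions with no disease at any other site. Table 4 counts loco-regional recurrence as a DFS event. Section 3.1.2 defines recurrence by a positive CT, or an equivocal CT backed by raised CEA and a positive PET. Section 3.1.1 also counts a new clinical sign, or two successive CEA rises above the normal limit.

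**The concern.** The stated field is narrower than the definitions that rest on it. A site that follows item 11 to the letter can randomise a patient whose pelvis has not been imaged for the trial, and can repeat that field through the first year. A relapse confined to the pelvis would then surface through CEA, symptoms, later spread, or whatever the site scans routinely.

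Three things are at stake.

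- **Who is NED.** The definition covers the whole body; the scan meant to verify it does not.
- **When relapse is dated.** One 12-week scan interval is about 2.76 months, or 46% of the 6-month control median assumed in the synopsis. If the pelvis is first imaged after randomisation, no baseline separates new disease from disease present at entry.
- **Uniformity.** Coverage is left to local practice at about 35 centres (synopsis; 25 to 40 in 6.1).

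**Working it through.** **1. Does any trial procedure require the pelvis?**

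| Stage | Section | Field stated |
|---|---|---|
| Screening | 8.1.1 item 11 | Chest and abdomen |
| Treatment phase, both arms | 8.1.2 | As baseline |
| Schedule footnote | Footnote c | None; same procedure throughout |
| End of treatment | 8.1.3 | None |
| Month 13 onward | 8.1.4 | Investigator's choice |
| General standard | 8.2.3.3 | Facility practice; minimal standards to follow |
| Eligibility criterion 7 | 6.2 | Modality only |

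None does. The baseline field carries forward explicitly only in the treatment phase.

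**2. Reproduce the design (synopsis and 4.2).** Inputs: two-sided alpha 0.05, power 90%, HR 0.6, 1:1 allocation, medians 6 and 10 months, uniform accrual A = 24 months, further follow-up F = 24 months, attrition 5%.

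- Schoenfeld events: 4 × (1.960 + 1.282)² / (ln 0.6)² = 161.1, rounded up to 162, against 164 stated.
- Power at 164 events: Φ(0.5108 × √164 / 2 − 1.960) = Φ(1.311) = 90.5%.
- Event probability by arm: 1 − [exp(−λF) − exp(−λ(A+F))] / (λA), with λ = ln 2 / median. This gives 0.979 for control and 0.908 for experimental, mean 0.943. Then 172 × 0.943 = 162 events.
- Attrition: 172 / 0.95 = 181.05, rounded up to 182.

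The plan's figures reproduce.

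**3. Events lost.** The share of relapses confined to the pelvis is an assumption: 3% to 10%, equal in both arms. HR among the counted events is held at 0.6.

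| Share lost | Events left | Power |
|---|---|---|
| 0% | 164 | 90.5% |
| 3% | 164 × 0.97 = 159 | Φ(1.261) = 89.6% |
| 10% | 164 × 0.90 = 148 | Φ(1.147) = 87.4% |

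**4. Events dated late.** Log-rank simulation: 172 patients, exponential times, the accrual and follow-up above, 1,500 runs per row, simulation error about 0.8 percentage points.

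| Share delayed | Delay | Power |
|---|---|---|
| 0% | none | 89.1% |
| 5% | 2.76 months (one scan) | 90.7% |
| 10% | 2.76 months | 88.1% |
| 10% | 5.5 months (two scans) | 88.1% |
| 20% | 5.5 months | 88.9% |

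There is no trend beyond simulation noise.

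**5. Extreme bound.** Step 3 only reduces the event count. If the affected patients instead stayed event-free and at risk until data cut-off, the arms would be diluted as well, and simulated power would be 58.5% at a 10% share and 37.3% at 20%. This is not realistic: a patient with an undetected pelvic relapse would still have an event at later spread, CEA rise, clinical sign or death. That makes late dating (step 4) the likelier consequence.

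**The case against.** A reader might infer that the trial images only the chest and abdomen, that every later scan inherits this field, and that NED is therefore not established in the pelvis. The documents do not go that far.

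- Item 11 sets what a site must do. It does not forbid a wider field. Criterion 7 and footnote c name no region, so sites may image the pelvis routinely.
- End-of-treatment and month-13-onward scans are not tied to the baseline field.
- A patient with known pelvic disease does not meet the NED definition in 2.4, and CEA must be normal at entry.
- The minimal standards promised in 8.2.3.3 may specify the pelvis; they cannot be seen here.
- New clinical signs, CEA rises and death all count as DFS events.

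A reader might also take section 2.3.1, item b ("staging extrahepatic disease with thoracic and pelvic CT"), as the protocol's own imaging rule. It sits in the background and concerns assessing resectability before surgery. It supports the point but does not contradict item 11 as one trial rule against another.

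Nor is bias between arms shown. The screening scan precedes randomisation, both arms repeat it, and randomisation is stratified by centre, so local scanning habits should fall about equally on the two arms.

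All of this stands, and it limits the point. It does not remove it, because each safeguard depends on local practice, on an unseen document, or on disease becoming apparent by another route. Centre stratification also does not equalise detection through symptoms: under 8.1.2 the experimental arm is seen weekly, then two-weekly, then monthly, and control every 12 weeks. Earlier dating of such relapses in the experimental arm is possible; the documents do not allow it to be quantified.

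**Conclusion.** The concern holds in limited form. Pelvic imaging is not required at screening or in the treatment phase, and the one field stated is too narrow for the NED definition and for a primary endpoint that includes loco-regional recurrence. NED verification and the dating of pelvic relapse therefore depend on local practice. The documents do not support saying that the pelvis goes unimaged in the trial as a whole, or that NED is not established there.

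The statistical effect is small. On an assumed pelvic-only share of 3% to 10%, power falls from 90.5% to between 89.6% and 87.4% if all those events are lost, and late dating alone makes no material difference. The sample size is unaffected. The case for the change rests on eligibility and endpoint ascertainment. It is best made before the first screening scan, because a missing pelvic baseline cannot be obtained afterwards.

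**What to change.** - In 8.1.1, item 11, state the field as chest, abdomen and pelvis.
- Repeat that field in schedule footnote c and in 8.2.3.3, so that the promised minimal standards carry it.
- Apply the same field to the end-of-treatment scan (8.1.3, item 6) and the follow-up scans (8.1.4, item 5), in both arms.

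The cost is a few words in the protocol and a longer field in the same scan session, with slightly more radiation and reading time. No extra visit is needed, and the event target and patient numbers stay as they are.

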	
crossover part of the study will be analyzed by means of proportional hazard time-depended analysis. Median disease-free survival will be calculated with the Kaplan-Meier method.
 
All statistical testing is two-sided at the nominal 5% significance level, with no adjustment for multiplicity. All patients who receive at least one regorafenib plus durvalumab dose will be included in the safety analysis.

Publication plan	
 - Timelines 2025 Q4 - Target Journals: Lancet, Lancet Oncology, JCO.

Table 1. SCREENING PHASE

	28 to 1 day before randomization ^d	
Informed consent	X	
Inclusion / Exclusion criteria	X	
General disease medical history	X	
Prior / Concomitant medications	X	
Complete physical examination	X	
ECOG PS	X	
Weight	X	
Vital Signs ^a	X	
12-lead ECG ^b	X	
Tumor imaging ^c	X	Must be performed within 10 weeks before D1C1. Tumor imaging can be accepted even if performed before the procedures to obtain NED status.
Hematology, chemistry, coagulation and pregnancy test ^d	X	
Biomarkers ^d	X	CEA and CA 19-9 must be on normal range
Histologic Confirmation	X	Only if surgery performed to obtain NED state, resection of the metastases must be R0

Table 2. Experimental arm

	From -7 days to Day 1 Cycle 1	Day 1 Cycle 1	Day 8, 15, 22 Cycle 1	Day 1 Cycle 2	Day 15 Cycle 2	Day 1 Cycle 3 and above up to 1-year (12 cycles)	QW12 from C1D1 (+/- 7 days)	End of treatment visit	Treatment discontinuation 30-days from last treatment or at initiation of other anticancer therapy (whichever occurs first)	Follow-up period ^g
Prior / Concomitant medications								X		X
Complete physical examination								X		X
Limited physical examination ^a		X	X	X	X	X				
ECOG PS		X	X	X	X	X		X		X
Weight		X		X		X				
Vital Signs ^a		X	X	X	X	X		X		X
12-lead ECG ^b								X		

Tumor imaging/ response assessments ^c							X	X		X
Hematology ^d	X		X	X	X	X		X		
Coagulation ^d	X							X		
Chemistry ^d	X		X	X	X	X		X		
Biomarkers ^d							X	X		X
Durvalumab Administration		X ^e		X ^e		X ^f				
Regorafenib Administration		X ^e		X ^e		X ^f				
AEs assessments	X		X	X	X	X		X	X	X
Survival and anti-cancer therapy									X	X

Table 3 - Control arm

	QW12 from C1D1 (+/- 7 days)	End of treatment visit	Treatment discontinuation 30-days from last treatment or at initiation of other anticancer therapy (whichever occurs first)	Follow-up period ^g
Prior / Concomitant medications	X	X		X
Complete physical examination	X	X		X
ECOG PS	X	X		X
Weight	X	X		
Vital Signs ^a	X	X		X

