7.1 Treatment Administered

Patients randomized and assigned to experimental arm will receive Regorafenib + durvalumab. Treatment will begin only after the patient has been randomized to the Treatment Group. Regorafenib 90 mg will be administered orally once daily for the first 21 days of each 28-day cycle, up to 1 year. Durvalumab (1500mg q4W IV infusion) will be administered every four weeks up to 1 year.

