
Abbreviations: BP=blood pressure; CTCAE=common terminology criteria for adverse events; G=Grade; Hg=mercury
 
If reductions are required resulting in a daily dose of less than 30 mg of regorafenib, regorafenib will be permanently discontinued. If BP remains controlled for at least one full cycle, dose re-escalation is permitted at the Investigator's discretion. Patients requiring a delay of > 4 weeks (28 days) (including the 1 week drug holiday) should discontinue regorafenib treatment. However, continuation of regorafenib may be considered if, in the Investigator's opinion, the patient may continue to benefit from the regorafenib treatment, and after consultation with the Medical Monitor.
	

Regorafenib Dose Modification Guidance, Non-Immune Toxicities: Liver Function Test Abnormalities^a

Increases in AST/ALT and/or bilirubin	1 st occurrence	Restart	Recurrence
AST and/or ALT ≤ to 5 x ULN, with normal AST and/or ALT at baseline	Continue dosing , with weekly monitoring of liver function until transaminases return to < 3 x ULN (< or equal to G1) or baseline.		
AST and/or ALT > 5 x ULN	Interrupt dosing , with weekly monitoring of liver function until transaminases return to < 3 x ULN or baseline.	If the potential to reinitiate regorafenib is considered to outweigh the risk of hepatotoxicity: reduce 1 dose level and measure serum transaminases weekly for at least 4 weeks.	Discontinue permanently
AST and/or ALT > 20 x ULN	Discontinue permanently and measure serum transaminases weekly until resolution.		

AST and/or ALT > 3 x ULN with concurrent total bilirubin > 2 x ULN	Discontinue permanently and measure serum transaminases weekly until resolution. Exception: participants with Gilbert's syndrome who develop elevated transaminases should be managed as per the above outlined recommendations for the respective observed elevation of ALT and/or AST.		

Abbreviations: ALT=alanine aminotransferase; AST=aspartate aminotransferase; ULN=upper limit of normal; G=Grade
 
If reductions are required resulting in a daily dose of less than 30 mg of regorafenib, regorafenib will be permanently discontinued.
 
Footnote:
 
a) If all values remain stable for 2 full cycles, dose re-escalation may be considered at the discretion of the Investigator. After re-escalation AST, ALT, bilirubin should be checked 2x/week for 2 weeks, followed by weekly assessments for at least 4 weeks.
			

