8 STUDY VISITS AND PROCEDURES

The timing of all assessments and procedures is detailed in Section 8.1; details of procedures and assessments to be done are provided in Section 8.2; Schedules of Events for pre-randomization, treatment periods and long term follow-up are provided in Table 1, Table 2 and Table 3.

Any procedures other than those indicated will be considered SoC of the facility, and not part of the study. Data from any CEA/CA 19-9 analyses or CT scans done as part of SoC procedures should be collected and recorded in the eCRF.

For all treatment arms

Tumor efficacy (RECIST) assessment dates are not affected by dose delays and remain as originally scheduled, as they are based on the date of randomization (not the date of therapy).

All other scheduled assessments must be performed relative to the start of the dosing cycle such that all laboratory procedures, etc. required for dosing should be performed within 3 days prior to dosing.

For durvalumab + regorafenib combination arms

Patients may delay dosing under certain circumstances.

- Dosing may be delayed per Toxicity Management Guidelines, due to either an immune or a non-immune-related AE.
- If dosing must be delayed for reasons other than treatment-related toxicity, dosing will resume as soon as feasible
- Dosing_intervals of subsequent cycles may be shortened as clinically feasible in order to gradually align treatment cycles with the schedule of tumor efficacy (RECIST). Subsequent time between 2 consecutive doses cannot be less than 22 days, based on the half-lives of durvalumab (see current Investigator Brochure for durvalumab).

Standard of Care Arm:

Patients may delay and subsequently resume dosing per local standard clinical practice.

If dosing must be delayed for reasons other than treatment-related toxicity, dosing will occur as soon as feasible.

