8.2.2.6 Adverse events (AEs)

After informed consent is obtained, AEs will be recorded continuously through the study conduct, and managed as outlined in Section 9 and according to the Safety Management Plan developed for this study. Events that occur prior to initiation of study treatment will be assessed as “not related” to study medication; AEs that occur after the first administration of study medication will be assessed as treatment-emergent AEs (TEAEs).

Adverse events will be categorised based on severity; relationship to study treatment and seriousness and according to National Cancer Institute's Common Terminology Criteria for Adverse Events (NCI CTCAE) Version 5.0.

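### The ±7-day visit window equals the weekly cycle-1 spacing, so read literally it allows up to 20 days between scheduled safety checks during the first regorafenib course

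*Combined protocol and SAP*

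**What the plan says.** Section 8.1.2 (Treatment Phase) says that experimental-arm patients "will undergo visits every week for the first cycle, every 2 weeks for the second cycle, and monthly thereafter". A few lines later it adds that "All visits have a window of" ±7 days, with no exception. Item 9 of the same section separately gives the 12-weekly tumour markers and scans their own ±7 days.

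Table 2 has a column headed "Day 8, 15, 22 Cycle 1" with no window. Haematology, chemistry, vital signs, limited examination, performance status and AE assessment are marked in it. The only window printed in that table's headings is on the column "QW12 from C1D1 (+/- 7 days").

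Section 7.1 says that regorafenib is "administered orally once daily for the first 21 days of each 28-day cycle".

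Four other provisions bear on the point:
- Section 8 says that laboratory procedures "required for dosing should be performed within 3 days prior to dosing".
- The liver-function table in Section 7.5.1 prescribes dosing decisions "with weekly monitoring of liver function until transaminases return to" a stated level.
- Section 8.2.2.6 says that "AEs will be recorded continuously through the study conduct".
- Footnote d to the schedule tables lets the investigator order additional blood tests.

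**The concern.** A window protects a schedule only if it is clearly narrower than the spacing between visits. Here both are 7 days, so adjacent weekly visits can be pulled apart or pushed together without any one of them being out of window.

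In Table 2 the Day 8, 15 and 22 visits are the only scheduled chemistry, haematology and vital-sign checks between the start of cycle 1 and Day 1 of cycle 2. They coincide with the first exposure to a combination for which Sections 4.3 and 7.1.1 say specific data are not available (Section 2.2 does cite one study in neuroendocrine tumours).

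Symptomatic events should still be reported. What could be found late is a silent change, such as an asymptomatic transaminase rise or hypertension. The regorafenib rules in Section 7.5.1 act on such findings only once a measurement has been taken, and the weekly liver monitoring there begins after a rise has been detected. A Day 15 visit held on Day 22 would be within window, so site monitoring might not flag it.

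**Working it through.** The plan states no maximum interval, so there is no figure of its own to reproduce. The check is arithmetic on the visit windows.

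**Inputs**
- Nominal visits: Days 8, 15 and 22 (Table 2).
- Window: ±7 days (Section 8.1.2).
- Regorafenib: Days 1-21 of a 28-day cycle (Section 7.1).
- Assumptions: Day 1 of cycle 2 is on its nominal Day 29, and every Table 2 visit is on its own day, in order, so that Day 1 < first < second < third < Day 29.

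**As planned.** 8−1 = 7, 15−8 = 7, 22−15 = 7, 29−22 = 7. Every interval is 7 days.

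**Permitted ranges at ±7 days**
- Day 8: 8−7 = 1 to 8+7 = 15.
- Day 15: 15−7 = 8 to 15+7 = 22.
- Day 22: 22−7 = 15 to 22+7 = 29.

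All three ranges contain Day 15.

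**Longest interval at ±7 days.** With the visits kept separate, the first can fall on Days 2-15, the second on Days 8-22 and the third on Days 15-28.
- Day 1 to first: at most 15−1 = 14.
- First to second: at most 22−2 = 20.
- Second to third: at most 28−8 = 20.
- Third to Day 29: at most 29−15 = 14.

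The maximum is 20 days. Visits on Days 2, 22 and 28 reach it, with no scheduled visit on Days 3-21.

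**Does another provision close the gap?**
- The 3-day rule in Section 8 concerns laboratory work required for dosing and is tied to the start of the dosing cycle. It does not fix the Day 8, 15 or 22 checks.
- Item 9 of Section 8.1.2 already covers the 12-weekly assessments, so the general sentence cannot be treated as merely repeating that window.
- Extra blood tests are optional.
- No minimum spacing or maximum interval is given for these visits.

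**With ±3 days.** The ranges are 5-11, 12-18 and 19-25, with no shared day. The longest interval between weekly visits is 18−5 = 13 (equally 25−12 = 13). Day 1 to the first visit is at most 11−1 = 10, and the third visit to Day 29 at most 29−19 = 10.

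**The case against.** The strongest reply is that the schedule on Days 2, 22 and 28 is hardly weekly. The specific frequency rule and the general window sit in the same section, and a reading that respects both lets single visits move while the weekly rhythm holds. Section 8.2 sends sites to Tables 1-3 as well as to Section 8.1, and Table 2 names the days without a window. This stands as evidence of intent: a loosely worded sentence is more likely than a deliberate ±7 days on weekly safety visits. It does not remove the problem, because the sentence covers all visits and the weekly wording sets no limit on the interval.

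Stronger readings are tempting, but the documents do not support them:
- **The number of checks is halved.** On Days 2-21 the example has 1 check (Day 2) against 2 planned (Days 8 and 15). Move the cutoff to Day 22 and it is 2 against 3. All three visits still take place before cycle 2. The interval is the sound measure; the count depends on the cutoff.
- **Ordinary slippage produces long gaps.** A uniform shift of 5 days gives Days 13, 20 and 27 or Days 3, 10 and 17. Spacing between weekly visits stays at 7 days and the longest interval is 12 days (13−1, or 29−17). Long gaps need shifts in opposite directions.
- **There may be no check at all on Days 2-21.** The arithmetic permits the Day 8 visit on Day 1, but that merges two visits that Table 2 lists separately.

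It is also fair to say that the documents give no basis for estimating how often a site would use this latitude, and that DFS, power and error rates are not affected.

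**Conclusion.** The point holds as a minor drafting fault with a safety aspect. Read literally, Section 8.1.2 allows up to 20 days between scheduled chemistry, haematology and vital-sign checks during the first regorafenib course, against 7 days as planned. The 20-day figure is a worst case under the literal window, with separate visits and cycle 2 starting on Day 29; it is not a forecast of site behaviour. A reader might infer that the protocol deliberately gives up weekly monitoring, or that toxicity would go unrecorded. Neither follows: the weekly wording and Table 2 show a tighter intent, AE recording is continuous, and additional blood tests are allowed. What remains is an inconsistency between text and table that leaves the early safety schedule without an enforceable limit.

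**What to change.** Keep the ±7-day sentence in Section 8.1.2 for all other visits, with Day 1 dosing visits also subject to the dosing rules in Section 8. Deleting the sentence, or confining it to the 12-weekly assessments, would take away the only stated window for other routine visits.

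Add one exception: the cycle-1 Day 8, 15 and 22 visits and the cycle-2 Day 15 visit have a narrower, non-overlapping window, for example ±3 days. Repeat it as a footnote to Table 2 so that table and text agree. The final width is for the sponsor's clinical team.

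The cost is one added sentence, one footnote and slightly less scheduling flexibility for sites.
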